**3.3.3.6 Urine PD Volume**

The Urine Volume is reported in the EDC along with starting and ending date/time. The volume will be normalized for the volume per hour ( $V_{upd}$ ):

$$V_{upd} = \frac{\text{Reported Volume}}{\frac{\text{Ending Datetime} - \text{Starting Datetime}}{60 \times 60}}$$

The 4-hour Urine PD volume on Day 0 will then be estimated as  $V_{upd} \times 4$

The 12-hour Urine PD volume on Day 1-3 will then be estimated as  $V_{upd} \times 12$

## EXTBIO EXT608-101 Statistical Analysis Plan, V2, 2023-JULY-04

Note: Assuming the value of datetime variable is in seconds. If either the date, time or volume is missing, this variable will also be set as missing. No imputation will be done.

### 3.3.4 Safety Variables

#### 3.3.4.1 *Adverse Events (AE)*

All observed or volunteered adverse events regardless in the treatment group or suspected causal relationship to the investigational device are captured in the EDC.

For all AEs, reformatting maybe applied and necessary transformation/Substitution may be needed as specified below:

- If an AE has known onset date but unknown onset time, then 12:00 will be used to substitute the onset time
  - The purpose of this substitution is for the determination of the TEAE
- If an AE has unknown onset date, no substitution will be done.

Treatment-emergent adverse event (TEAE) is defined as a post-baseline adverse event with onset date and time after the initiation of study treatment.

- Baseline is the IP administration date and time
- In this study, TEAE are the AEs that occur after the first successful IP administration.
  - If the AE has an unknown onset date, it will be assumed to be non-TEAE unless the investigational site confirms it is an TEAE

AE Coding:

- AE will be coded with latest available, at the time of coding, MedDRA code.

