## 6.10 Safety Variables and Safety Reporting

### 6.10.1 Adverse Events

#### 6.10.1.1 Adverse Events

An Adverse Event (AE) is defined as any untoward medical occurrence in a participant or clinical investigation participant administered a pharmaceutical product and which does not necessarily have to have a causal relationship with this treatment. An AE can therefore be any unfavorable and unintended sign (including an abnormal laboratory finding, for example), symptom, or disease temporally associated with the use of a medicinal product, whether or not it is considered related to the medicinal product.

Adverse events will be collected from the time informed consent is signed and until the Follow-Up or Early Termination visit.

All participants will be queried, using non-leading questions, about the occurrence of AEs at each study visit. When possible, a constellation of signs and/or symptoms should be identified as one overall event or diagnosis. All AEs for randomized subjects will be recorded in the eCRF and the subject's source documents. Adverse events for subjects who are screened but not subsequently randomized in the study will be recorded only in the subject's source documents. The following data should be documented for each AE:

- Description of the events
- Classification of “serious” or “not serious”
- Date of first occurrence and date of resolution (if applicable)
- Severity
- Causal relationship to study drug
- Action taken
- Outcome
- Concomitant medication or other treatment given

Adverse events will be rated a mild, moderate or severe intensity using the following definitions:

- Mild: “Mild” events are usually transient and do not interfere with the participant’s daily activities.
- Moderate: “Moderate” events introduce a low level of inconvenience or concern to the participant and may interfere with daily activities.
- Severe: “Severe” events interrupt the participant’s usual daily activities.

The causality will be rated in the following categories:

- Unlikely: An “unlikely” relationship suggests that only a remote connection exists between the investigational study product and the reported AE. Other conditions, including chronic illness, progression or expression of the disease state or reaction to concomitant medication, appear to explain the reported AE.

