#### **3.4.5.1 Adverse Event**

All AE (including TEAE and non-TEAE) will be listed.

Unless there are less than or equal to 5 TEAE in the whole study period, TEAE will be summarized as followed:

All TEAE will be presented with the number and percentage of participants and events (counts only), by System organ class (SOC) and by Preferred Term (PT).

The same summary will also be presented for the following group:

- All TEAE that may have a relationship to the study medication (i.e., site categorize the relationship in EDC as either Related, Probable, Possible, or Unlikely)
- Intensity Categorization Groups: Mild, Moderate and Severe
- Serious TEAE (SAE)

An overview of the above summary with count and percentage of participants will also be provided.

Any non-TEAE will be provided as listing only.

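### For adverse events dated Day 0 with no onset time, the SAP's 12:00 substitution sets treatment-emergent status by whether the dose came before noon, not by the order of events

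*SAP*

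**What the plan says.** SAP 3.3.4.1 defines the term: "Treatment-emergent adverse event (TEAE) is defined as a post-baseline adverse event with onset date and time after the initiation of study treatment". The reference point is also explicit: "Baseline is the IP administration date and time". For a missing time the SAP says: "If an AE has known onset date but unknown onset time, then 12:00 will be used to substitute the onset time". It adds the reason: "The purpose of this substitution is for the determination of the TEAE".

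A missing date has its own rule: "If the AE has an unknown onset date, it will be assumed to be non-TEAE unless the investigational site confirms it is an TEAE". No such site confirmation is offered when only the time is missing.

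On reporting, SAP 3.4.5.1 summarises TEAEs by system organ class and preferred term, by relationship, by intensity and by seriousness. For the rest it says: "Any non-TEAE will be provided as listing only".

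Protocol 6.10.1.1 lists the data to document for each AE. The only timing item is "Date of first occurrence and date of resolution (if applicable"). On the collection window it says: "Adverse events will be collected from the time informed consent is signed and until the Follow-Up or Early Termination visit". Day 0 events from before the dose are therefore recorded as well as those from after it.

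**The concern.** On Day 0 the order of event and dose is the whole question, and the substituted time carries no information about that order. The same event, in the same relation to the dose, can be a TEAE in a participant dosed at 11:00 and a non-TEAE in a participant dosed at 13:00. The result can also contradict the SAP's own plain statement, in the same section, that TEAEs are the AEs occurring after the first successful administration.

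What is at stake is the first primary measure, which covers the incidence, nature and severity of AEs and withdrawals due to TEAEs. Day 0 is also the day of closest observation after a single injection. An event called non-TEAE by the noon rule leaves every TEAE table and survives only in a listing. SAP 3.4.5.1 produces the TEAE tables only if there are more than 5 TEAEs in the study, so in a quiet study a few reclassified events could also decide whether the tables are produced at all.

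**Working it through.** No sample size or power figure is involved. The check is to apply the SAP rule as written.

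**Inputs**
- Imputed onset: 12:00 on the recorded onset date (SAP 3.3.4.1).
- TEAE if imputed onset is later than the date and time of dosing (SAP 3.3.4.1).
- Dosing is on Day 0 by definition (SAP 3.3.2.1).
- 3 active and 1 placebo participant per cohort, up to 6 planned cohorts (Protocol 3.1.1), with placebo pooled across cohorts (Protocol 8.3).
- Clock time of dosing: not readable in the documents. Assumed range 08:00 to 15:00.

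**Step 1: which days are affected.** An untimed AE dated Day -1 is placed at noon on the day before dosing. It is a non-TEAE for any dose time, which is correct. An untimed AE dated Day 1 is placed at noon on the day after dosing. It is a TEAE for any dose time, also correct. Only Day 0 can go wrong.

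**Step 2: untimed AE dated Day 0.**

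| Assumed dose time | Imputed onset after dose? | Call | Which events are called wrongly |
|---|---|---|---|
| 08:00, 09:00, 10:00, 11:00, 11:59 | yes | TEAE | those that began before the dose |
| 12:00 | no (equal, not after) | non-TEAE | those that began after the dose |
| 12:01, 13:00, 14:00, 15:00 | no | non-TEAE | those that began after the dose |

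The call changes once, at a dose time of 12:00, and never depends on the true onset. A Day 0 AE with a recorded time is classified correctly.

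**Step 3: size for one participant.** Assume the participant has no other TEAE.
- Dose arm with one cohort: 1/3 = 33 percentage points.
- Dose given to two cohorts, as the escalation rules in Protocol 3.1.5 allow: 1/6 = 17 percentage points.
- Pooled placebo if all six cohorts are run: 1/6 = 17 percentage points.

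**Step 4: share of untimed Day 0 AEs called wrongly.** This needs an assumption about true onset. Purely for illustration, let onset be uniform over the 24 hours of Day 0 and let d be the dose hour. The share is d/24 for d before 12, and (24 − d)/24 for d at or after 12. This gives 8/24 = 33% at 08:00, 12/24 = 50% at noon and 9/24 = 38% at 15:00. Real onsets are unlikely to be uniform. The figures show only that the rule is not close to accurate at any plausible dose time under that assumption.

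**The case against.** The best case for the plan is that the rule will seldom act, and then mostly without harm. Several parts of it stand.

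- **Missing times may be rare.** A reader might infer from Protocol 6.10.1.1 that date-only recording is the norm. The documents do not show that. The list is not an eCRF specification, and the SAP's wording treats a missing time as an unknown value, which suggests that a time field exists. Participants are also inpatients on Day 0 with closely timed assessments (SAP Table 2).
- **Injection site reactions do not disappear.** A reader might picture an arm whose three reactions all vanish, showing 0/3 instead of 3/3. The documents do not support that. Protocol 6.4 requires positive findings to be photographed with date and time. SAP 3.4.5.5 summarises tenderness, pain score, edema and erythema by arm with no TEAE filter, and the percentage with reactions is a separate primary measure.
- **The direction is not known.** A reader might conclude that the plan systematically under-counts. That would need dosing at or after noon. Protocol 6.8.2.2 has a first morning void before dosing and a collection from 4 hours post-dose until bedtime. This fits morning dosing without proving it, and the Day 0 procedure text is not shown in the public copy. With dosing before noon the error runs towards over-counting.
- **Escalation is not shown to be affected.** Protocol 3.1.4 defines a potential dose-limiting toxicity as a TEAE, but the decision rules in 3.1.5 use Grade 3 AEs suspected related to study drug and serum calcium. Handling of potential dose-limiting toxicities is left to a Safety Plan that is not among the documents.
- **The unknown-date rule has a remedy.** Its default is non-TEAE, but the site can confirm otherwise. Reversing that default is a preference for consistency, not the correction of an error.

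These points limit how often the fault matters. None of them gives an untimed Day 0 event a route to the correct call, because site confirmation applies to unknown dates only.

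**Conclusion.** The point holds as a defect in a stated rule. For AEs dated Day 0 with no onset time, SAP 3.3.4.1 assigns treatment-emergent status by dose time against noon. Post-dose events are lost from the TEAE summaries if the dose is at or after 12:00. Pre-dose events are added if it is before.

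One participant misclassified in this way, with no other TEAE, moves a single-cohort dose arm by 33 percentage points. That is the effect of one such case and not an estimate of how often it happens. The frequency depends on whether the eCRF captures onset time, and the direction depends on when doses are given. The documents settle neither. All AEs remain visible in the listings, which in a study of about 24 to 30 participants is a real safeguard.

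Severity is minor to moderate: the consequence is conditional, but the rule cannot be relied on for the day of dosing and is easy to replace.

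**What to change.** **SAP 3.3.4.1.** Replace the 12:00 rule: an AE dated on the day of dosing with no onset time is a TEAE unless the site records that it began before dosing. For untimed events this changes the default call where the dose was at or after 12:00. Where the dose was before 12:00 it keeps the present call but lets the site correct it.

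**Protocol 6.10.1.1 and eCRF.** Require an onset time, or a before/after-dose flag, for AEs that start on Day 0.

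**Optional, for consistency.** Treat an AE with an unknown onset date as a TEAE unless its stop date or the site shows that it began before dosing.

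**Cost.** A short SAP edit and one eCRF field. If onset times are already collected, the SAP edit costs almost nothing. The downside is that a few pre-dose Day 0 events may be counted as TEAEs when the flag is left blank. In a first-in-human safety study that is the more acceptable error.

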Se-Ca	Serum calcium
SERM	Selective estrogen receptor modulator

Study product	The formulated product as delivered to the participant containing either test (active) drug or control (placebo). The term may refer to either.
T 1/2	Serum half-life of a drug; the time it takes for the concentration of the drug to be reduced by half
TEAE	Treatment Emergent Adverse Event
TdP	Torsade de pointes; refers to a specific abnormal heart rhythm
T max	The time it takes to reach maximum drug concentration
ULN	Upper Limit of Normal
VAS	Visual Analog Scale
Vz/F	Apparent distribution volume
WBC	White Blood Cell count with differential count

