##### 3.1.4 Dose Limiting Toxicity (DLT) Criteria

A potential DLT is defined as any of the following EXT608 TEAEs that occurs during the DLT period, graded according to the NCI Common Terminology Criteria for Adverse Events (CTCAE), Version 5.0 (2):

- Grade = 3 TEAE
- Grade = 3 anemia
- Grade = 3 AST/ALT elevation; and/or
- Grade = 2 AST/ALT elevation and Grade = 2 Bilirubin elevation

- Grade = 3 QTc prolongation
- Grade = 3 Hyper- and/or Hypotension
- Grade = 2 Hyperparathyroidism
- Grade = 2 Hyperthyroidism
- Grade = 3 Hypercalcemia
- Grade = 3 Hypocalcemia
- Grade = 3 Hypophosphatemia
- Grade = 3 Hypomagnesemia
- Grade = 3 Creatinine increased

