## **6.3 Physical Exam**

### **6.3.1 Complete Physical Exam**

A complete physical exam will be performed at the screening and the last visit either when the participant has completed the full study or at an early termination. The physical exam will include: general appearance; head, eyes, ears, nose, throat, chest, lungs, heart, abdomen, musculoskeletal, skin neurological including reflexes. At the screening exam, any abnormalities found will be recorded in the eCRF under the medical history in the appropriate category. Any new findings at the last visit will be captured as an adverse event on the CRF for adverse events. The eCRF will thus not include any specific pages for physical exam.

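### The SAP defines TEAEs by onset alone, and neither document says how a pre-dose adverse event that worsens after dosing is classified or recorded, so it can drop out of the TEAE tables

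*SAP*

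**What the plan says.** **Definition.** SAP 3.3.4.1 states: "Treatment-emergent adverse event (TEAE) is defined as a post-baseline adverse event with onset date and time after the initiation of study treatment". It restates the rule as "In this study, TEAE are the AEs that occur after the first successful IP administration". The same section substitutes noon for an unknown onset time, for the purpose of deciding which events are TEAEs, so onset is the deciding variable. The protocol gives no definition; its abbreviation list only spells out "Treatment Emergent Adverse Event". SAP 1.4 declares no changes from the protocol's statistical section.

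**Collection.** Protocol 6.10.1.1 says "Adverse events will be collected from the time informed consent is signed and until the Follow-Up or Early Termination visit". For each event the site documents, among other items, a severity and "Date of first occurrence and date of resolution (if applicable". There is no instruction on what to do when an event already recorded gets worse. For the physical examination, protocol 6.3.1 says "Any new findings at the last visit will be captured as an adverse event", and it does not mention worsening of a finding already present at screening.

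**Reporting.** Under SAP 3.4.5.1 all AEs are listed, but only TEAEs are tabulated: overall by system organ class and preferred term, and again by relationship, intensity and seriousness. Non-TEAEs get a listing and nothing else.

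**Dose-limiting toxicity.** Protocol 3.1.4 says "A potential DLT is defined as any of the following EXT608 TEAEs that occurs during the DLT period". The decision tree in protocol 3.1.5 works with Grade 3 AEs suspected to be related to study drug and does not require them to be treatment-emergent.

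**The concern.** An event that is mild before the dose and severe or serious after it may be an effect of the drug. An onset-only rule cannot see it, because the post-dose change lies in the severity and the onset date stays where it was. If the event is kept on one record, its date of first occurrence precedes dosing and it is classed as a non-TEAE.

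The first primary measure is the incidence, nature and severity of AEs, together with withdrawals due to TEAEs. The SAP's only tabulation of that measure is the set of TEAE tables. A worsened pre-dose event would be missing from them, and a withdrawal caused by it would not count as due to a TEAE. With three EXT608 participants per dose level, one missing participant changes the picture at that dose.

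The outcome also depends on data-entry habit. Two identical clinical courses could be classified differently, one as a TEAE and one not, according to whether the site opened a second record.

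**Working it through.** The documents state no figure on this point, so there is none to reproduce. The check is to follow one event through the rules and then size the effect.

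**Step 1. Can pre-dose AEs exist in the data?** Yes. Collection starts at consent (protocol 6.10.1.1), and screening may fall up to 28 days before dosing (protocol 3.1.6).

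**Step 2. How is a worsened event classified?**
- *One record kept:* onset is before dosing, so it is a non-TEAE under SAP 3.3.4.1.
- *New record opened for the worsening:* onset is after dosing, so it is a TEAE.

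No text in either document requires or forbids the second course.

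**Step 3. Where does the non-TEAE appear?** In the AE listing only. It is absent from the SOC/PT, relationship, intensity and serious-TEAE tables (SAP 3.4.5.1).

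**Step 4. Is it a potential DLT?** Protocol 3.1.4 takes potential DLTs from TEAEs. The protocol does not define the term, so this step assumes that the SAP definition applies. On that assumption the event is outside the potential-DLT definition. Under protocol 3.1.5 the same event, if Grade 3 and suspected related, is within the wording of the decision tree. The two sections use different event sets.

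**Step 5. Size.** Inputs: 3 EXT608 participants per cohort and up to 6 cohorts (protocol 3.1.1), so 6 × 3 = 18 on EXT608. For illustration, suppose one EXT608 participant has such an event and no other event of that type occurs. The intervals are exact (Clopper-Pearson) 95% intervals.

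| | Onset-only rule, one record | Worsening counted |
|---|---|---|
| One dose level | 0/3 = 0% (0 to 70.8%) | 1/3 = 33.3% (0.8 to 90.6%) |
| Six cohorts | 0/18 = 0% (0 to 18.5%) | 1/18 = 5.6% (0.1 to 27.3%) |

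**Step 6. How likely is at least one case?** The documents give no rate. With an assumed per-participant chance p, the probability of at least one among 18 is 1 − (1 − p)^18:
- p = 1%: 1 − 0.99^18 = 16.5%
- p = 2%: 30.5%
- p = 5%: 60.3%
- p = 10%: 1 − 0.90^18 = 85.0%

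The range of p is an assumption, and the width of the result shows that the frequency cannot be settled from the documents.

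**The case against.** **Recording practice.** The AE definition in protocol 6.10.1.1 is broad enough for a site to enter a post-dose worsening as an AE in its own right, and asking for a date of first occurrence does not forbid that. Collection detail may also sit in the data management plan (protocol 10.2), which is not available. This stands: a reader might infer that worsened events can never reach the TEAE tables, and the documents do not support that. They support only that no rule is stated.

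**Dose escalation.** A reader might also infer that such events are lost to a DLT count and so to escalation decisions. The documents do not support that either. They contain no DLT count. The rules that count events are in protocol 3.1.5 and refer to related Grade 3 AEs, which a worsened pre-dose event could meet. DLT evaluation is left to a Safety Plan (protocol 4.3.1.3) that is not available.

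**Other routes of capture.** Laboratory, vital-sign and ECG changes are summarised against baseline whatever the AE onset. All SAEs must be reported within 24 hours (protocol 6.10.1.4). All AEs are listed, and with about 24 to 30 participants each can be read individually. This narrows the gap mainly to clinical, symptomatic AEs, but it does not put the event back into the TEAE, intensity or serious-TEAE tables.

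**Size.** The 33.3 points are simply 1/3 and would apply to any misclassified event. Participants must be in good general health (protocol 4.1), which should limit AEs ongoing at dosing, and no formal hypothesis test is planned. All of this is true. It limits the expected number of cases but leaves the definition incomplete.

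**Conclusion.** The point holds as a gap in a definition and its matching recording rule. Followed as written, and unless the site opens a new AE record, the SAP leaves post-dose worsening of a pre-dose AE out of every TEAE table. The tabulated incidence or severity in any arm can then only be too low. One affected participant is 33.3 percentage points at a dose level and 5.6 points over 18 EXT608 participants, provided that participant has no other event counted in the same row. The frequency is unknown.

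The link to DLTs is conditional on carrying the SAP definition into protocol 3.1.4. What can be said firmly is that protocol 3.1.4 (TEAEs) and 3.1.5 (related Grade 3 AEs) use different event sets. It does not follow that escalation decisions would miss such an event.

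This should be corrected because it touches a primary safety measure in a first-in-human study and costs very little. It does not call the design into question.

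**What to change.** 1. **SAP 3.3.4.1:** define a TEAE as an AE with onset after dosing, or with onset before dosing that increases in severity or becomes serious after dosing. Align the restatement in the same section.
2. **Protocol 6.10.1.1 and the CRF completion instructions:** require post-dose worsening of an existing AE to be entered as a new AE line with its own start date and severity.
3. **Protocol 3.1.4 and 3.1.5:** reconcile the event sets, so that it is clear whether potential DLTs and the decision tree refer to the same events. Which set applies is for the sponsor and the DMB to settle.

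The cost is one SAP sentence, one recording instruction and a clarification in the protocol. If participants have already been dosed, the site should also check each AE that was ongoing at dosing for later worsening. No change to sample size, visits or assessments is needed.

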## **6.4 Injection Site Assessment**

The intended injection site in the abdomen will be photographed prior to injection.

The injection site assessment includes evaluation of erythema, edema and any tenderness. The size of any erythema is measured with shortest and longest size in mm, and edema similarly in size and in addition the tallest height above surrounding skin. The measurement data are recorded in the EDC.

Any positive finding will be photographed with clear labeling next to the lesion of participant ID, date and time.

Following a positive finding the injection site will be photographed daily in the inpatient period, and subsequently at the clinics visits until resolved.

Minimally, the photographs

1. prior to injection,
2. when the event is at highest intensity, and
3. when resolved or stabilized

will be uploaded in the EDC.

A Visual Analog Scale (VAS) will be used for evaluation of injection site pain. A copy of the VAS is in [Appendix 2](#).

Positive events will furthermore be recorded as AEs.

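### SAP 3.3.4.1 counts an AE as treatment-emergent only if onset is after dosing and has no rule for a tie, so an immediate reaction recorded at the dosing minute drops out of the TEAE tables

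*SAP*

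**What the plan says.** SAP 3.3.4.1 states the rule twice. The general definition is "Treatment-emergent adverse event (TEAE) is defined as a post-baseline adverse event with onset date and time after the initiation of study treatment", with the anchor "Baseline is the IP administration date and time". The study-specific bullet is that "TEAE are the AEs that occur after the first successful IP administration".

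Two special cases follow, both for missing information:

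- If the onset date is known but the time is not, "then 12:00 will be used to substitute the onset time".
- For a missing date: "If the AE has an unknown onset date, it will be assumed to be non-TEAE unless the investigational site confirms it is an TEAE".

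SAP 3.4.5.1 then divides the reporting. On one side, "All AE (including TEAE and non-TEAE) will be listed". The tables by SOC and PT, and the same tables by relatedness, intensity and seriousness, are built from TEAEs alone, and "Any non-TEAE will be provided as listing only".

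Study treatment is a single subcutaneous injection. For the injection-site assessment, Protocol 6.4 adds: "Positive events will furthermore be recorded as AEs". That wording came from an amendment made on an FDA recommendation.

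**The concern.** With a single injection, some reactions begin as the needle goes in: pain at the site, or an immediate systemic or vasovagal response. If the site records the onset as the dosing time, onset and anchor are equal. Equal is not after, so the literal rule puts the event with those that began before dosing, although it may have been caused by the injection.

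At stake is the completeness of the TEAE tables, which are the SAP's only tabulation of AEs by arm and by SOC/PT, relatedness, intensity and seriousness. With three active participants per cohort, one misclassified participant can change a dose arm's incidence visibly. SAP 3.4.5.1 also drops the TEAE summary when the study has five or fewer TEAEs, so a tie could in principle decide whether the tables are produced.

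**Working it through.** The documents state no figure on this point, so there is none to reproduce. The check applies the rule and then sizes one misclassification.

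**Step 1: apply the rule.** Take an illustrative dose at 09:00 and compare the SAP's rule (onset > dose time) with an inclusive rule (onset ≥ dose time).

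| Recorded onset | SAP rule | Inclusive rule |
|---|---|---|
| 08:59 | non-TEAE | non-TEAE |
| 09:00 (tie) | non-TEAE | TEAE |
| 09:01 | TEAE | TEAE |

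Only the tie changes class.

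**Step 2: look for another rule that catches the tie.** The 12:00 substitution needs an unknown time, and site confirmation needs an unknown date. An event with both known meets neither condition.

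**Step 3: are times held to the minute?** A substitute value of 12:00 implies a clock time in hours and minutes, and the SAP treats an unknown time as the exception. Protocol 7.2 counts study activities in minutes, hours or days from dosing. Against this, the AE data list in Protocol 6.10.1.1 asks for the date of first occurrence and names no time. Minute-level recording is therefore an assumption.

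**Step 4: weight of one participant.** Inputs are up to 6 cohorts, 3 active and 1 placebo in each (Protocol 3.1.1), and placebo pooled across cohorts (Protocol 8.3).

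- Dosed if all six cohorts run: 6 × 4 = 24. Pooled placebo: 6 × 1 = 6.
- One participant in a dose arm of 3: 100/3 = 33.3 points.
- One participant in pooled placebo: 100/6 = 16.7 points.

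These shifts apply only when the tied event is the participant's sole TEAE.

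**Step 5: chance of at least one tie.** The per-participant probability q is not in the documents and is assumed. The formula is 1 − (1 − q)^n.

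| Assumed q | n = 3 (one dose arm) | n = 24 (all dosed) |
|---|---|---|
| 1% | 1 − 0.99³ = 3% | 1 − 0.99²⁴ = 21% |
| 5% | 1 − 0.95³ = 14% | 1 − 0.95²⁴ = 71% |
| 10% | 1 − 0.90³ = 27% | 1 − 0.90²⁴ = 92% |

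Steps 4 and 5 should not be multiplied together. Step 5 counts anyone with a tied event, while step 4 needs a participant with no other TEAE.

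**The case against.** The best defence is that pain caused by an injection begins after the injection was initiated, so in substance it already meets the main definition. The exclusion arises only if both times fall in the same recorded minute and a program applies a strict inequality. No program or EDC specification is in the documents. This stands as far as it goes, but the second bullet, which refers to a successful administration, points the other way. A rule that can be read both ways needs an explicit answer for ties.

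Several stronger readings are tempting, and the documents do not support them:

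- *The first primary measure is understated.* It is worded as incidence, nature and severity of AEs; treatment-emergent qualifies only withdrawals (Protocol 2.1, SAP 1.2.1). A tied event is still an AE and is still listed.
- *Injection-site reactions are lost.* They have their own primary measure. SAP 3.4.5.5 summarizes VAS, tenderness, edema and erythema by arm with no TEAE filter, so a finding present at an assessment is lost from the TEAE tables only. Immediate systemic reactions are not covered there.
- *Escalation or DLT decisions are affected.* The tree in Protocol 3.1.5 uses related Grade 3 AEs, so the tie does not touch it. Protocol 3.1.4 does define potential DLTs through TEAEs, but it does not adopt the SAP's timestamp comparison. Protocol 4.3.1.3 sends the evaluation to the DMB under a Safety Plan that is not among the documents.
- *The drug is made to look better than placebo.* Placebo participants are injected too and are subject to the same rule. Absolute TEAE counts can only fall, but no direction of bias between groups is shown.

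**Conclusion.** The gap is real and narrow. As written, a known onset equal to the dosing time is a non-TEAE, and no other provision rescues it. Such an event stays in the AE listing but leaves every TEAE table. The loss matters most for immediate systemic reactions, which have no separate summary.

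The conclusion rests on two assumptions: onset and dosing are recorded to the minute, and the rule is programmed literally. How often ties would occur is unknown, so the chances of 21%, 71% and 92% illustrate assumed rates and are not forecasts. The shift of 33 points in a dose arm, or 17 points in pooled placebo, is the size of one case in which the tied event is the participant's only TEAE. The correction is worth making because ties are foreseeable in a single-injection study and the change is nearly free.

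**What to change.** In both statements of the rule in SAP 3.3.4.1, change 'after' to 'at or after' the IP administration date and time. Add that a same-minute event is classed as non-TEAE only when the site documents that it began before the injection.

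The cost is a wording change and one comparison operator in the program. The small downside is that an event starting just before the injection, within the same minute, would count as a TEAE unless the site says otherwise.

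The change does not settle a separate matter: under either rule, a Day 0 event of unknown time in a participant dosed after noon is set to 12:00 and so becomes a non-TEAE.
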